RO expressed as a percentage will be calculated for each subject and each postdose scan. Spatial normalization of the PET scan to a brain atlas template will be performed using a corresponding MRI scan. All PET parameters will be calculated globally, for the whole brain, and for specific predefined brain areas.

The occupancy data for the study will be combined with the plasma concentration of pridopidine and used to derive the in vivo affinity of pridopidine for the S1R and the time-course of the occupancy of S1R by pridopidine.

Test-retest variability of (S)-(-)-[¹⁸F]fluspidine uptake will be estimated using 2 baseline (S)-(-)-[¹⁸F]fluspidine scans in up to 6 subjects. This will be used to calculate the uncertainty of the RO estimate.

The analysis using [¹⁸F]fallypride will be similar to that using (S)-(-)-[¹⁸F]fluspidine.

For calculation of BP_{ND} and RO for [¹⁸F]fallypride a tissue reference model can be used using the cerebellum as reference region without specific binding.

Pharmacokinetic Analysis: Pharmacokinetic parameters will be calculated for pridopidine and its metabolite TV-45065 in the plasma using non compartmental methods, when possible. No formal statistical analyses of the pharmacokinetic data will be performed. All data will be listed and summarized descriptively by cohort (dose) and status (healthy subject or HD patient) and presented in tabular and graphical form where appropriate.

Pharmacokinetic/Pharmacodynamic Analysis:

The relationship between the pridopidine plasma concentrations and the RO will be explored graphically. If possible, an exposure-response model will be developed to quantitatively define the relationship between RO and pridopidine exposure. It will be based on the following E_{max} model (equation) to fit the pharmacokinetic-pharmacodynamic (PK/PD) data.

$$E = \frac{E_{\max} \times C}{EC_{50} + C}$$

Where E represents the receptor occupancy (%); C is the plasma concentration (ng/mL) corresponding to the receptor occupancy E; E_{max} is an asymptote representing the maximum receptor occupancy (%); EC₅₀ is the plasma concentration (ng/mL) corresponding to 50% of E_{max}.

Two additional parameters derived to characterize various levels of receptor occupancy are:

- EC₈₀ - the plasma concentration (ng/mL) corresponding to 80% of E_{max}. It is calculated directly from the equation by substituting E=80% of E_{max} and then solving for C.
- EC_{opt} - plasma concentration (ng/mL) corresponding to optimal receptor occupancy. EC_{opt} was defined as the lowest observed plasma concentration that achieved the model estimated E_{max}.

Safety Analyses:

All adverse events will be coded using the Medical Dictionary for Regulatory Activities (MedDRA). Each subject will be counted only once in each preferred term or system organ class (SOC) category for the analyses of safety. Summaries will be presented for all adverse events (overall and by severity), adverse events determined by the investigator to be related to study treatment (ie, reasonable possibility) (defined as related or with missing relationship) (overall and by severity), serious adverse events, and adverse events causing withdrawal from the study. Summaries will be presented by treatment group and for all subjects. Subject listings of serious adverse events and adverse events leading to withdrawal will be presented.

Changes in laboratory and vital signs measurement data will be summarized descriptively. All values will be compared with predefined criteria to identify potentially clinically significant values or changes, and such values will be listed.

The use of concomitant medications will be summarized by therapeutic class using descriptive statistics.

Concomitant medications will include all medications taken while the subject is treated with study drug.

For continuous variables, descriptive statistics (n, mean, standard deviation, median, minimum, and maximum) will be provided for actual values and changes from baseline to each time point. For categorical variables, subject counts and percentages will be provided. Descriptive summaries of serious adverse events, subject withdrawals due to

adverse events, and potentially clinically significant abnormal values (clinical laboratory or vital signs) based on predefined criteria will be provided as well.

If any subject dies during the study, a listing of deaths will be provided and all relevant information will be discussed in the subject narrative included in the clinical study report.

Tolerability Variables and Analysis:

Subject tolerability assessments (the number [%] of subjects who fail to complete the study, number [%] of subjects who fail to complete the study due to adverse events, and the number of subjects who experience treatment-emergent adverse events) will be summarized.

Pharmacogenetic and Biomarker Analysis:

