1.4.2.2. Risks of [¹⁸F]fluspidine

The mass dose of [¹⁸F]fluspidine proposed for use in this study is not sufficient to elicit a pharmacologic response to the agent. To date, no untoward effects have been attributed to [¹⁸F]fluspidine in the ongoing clinical trial; however, it is possible that there are unknown risks with the use of this tracer as it has not been fully characterized at this time.

When using a tracer administered activity of 300±30 MBq per PET session, the radiation exposure due to the cumulative [¹⁸F]fluspidine dose for all PET sessions will not exceed 20 mSv which is the maximum specified by the German Radiation Protection Ordinance (Strahlenschutzverordnung §24) for radiation exposure of healthy subjects in medical research. The conversion factor for the effective dose to humans is 22.1 µSv/MBq ([Sattler et al 2016](#); [Kranz et al 2016](#)) resulting in an effective dose of 7.3 mSv if the maximum considered activity of 330 MBq (300+10%) would be administered.

A washout period of 7 days will occur between any necessary repeat PET sessions, if applicable.

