7.1.2. Recording and Reporting of Adverse Events

For recording of adverse event, the study period is defined for each subject as that time period from signature of the informed consent form to the end of the follow-up period. The follow-up period is defined as 7 days after the last dose of study drug.

All adverse events that occur during the defined study period must be recorded on the source documentation and transcribed to the CRF, regardless of the severity of the event or judged relationship to the study drug. For serious adverse events, the serious adverse event form must be completed and the serious adverse event must be reported immediately (see Section 7.1.5.3.1). The investigator does not need to actively monitor subjects for adverse events once the study has ended. Serious adverse events occurring in a subject after the treatment of that subject has ended should be reported to the sponsor if the investigator becomes aware of them, following the procedures described in Section 7.1.5.3.1.

At each contact with the subject, the investigator or designee must question the subject about adverse events by asking an open-ended question such as “Have you had any unusual symptoms or medical problems since the last visit? If yes, please describe”. All reported or observed signs and symptoms will be recorded individually, except when considered manifestations of a medical condition or disease state. A precise diagnosis will be recorded whenever possible. When such a diagnosis is made, all related signs, symptoms, and any test findings will be recorded collectively as a single diagnosis on the CRF and, if it is a serious adverse event, on the serious adverse event form.

The clinical course of each adverse event will be monitored at suitable intervals until resolved, stabilized, or returned to baseline; or until the subject is referred for continued care to a health care professional; or until a determination of a cause unrelated to the study drug or study procedure is made.

The onset and end dates and times, duration, action taken regarding study drug, treatment administered, and outcome for each adverse event must be recorded on the source documentation and transcribed to the CRF.

The relationship of each adverse event to study drug and study procedures, and the severity and seriousness of each adverse event, as judged by the investigator, must be recorded as described below.

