7.1.4. Relationship of an Adverse Event to the Study Drug

The relationship of an adverse event to the study drug is characterized as follows:

Term	Definition	Clarification
No reasonable possibility (not related)	This category applies to adverse events that, after careful consideration, are clearly due to extraneous causes (disease, environment, etc) or to adverse events that, after careful medical consideration at the time they are evaluated, are judged to be unrelated to the study drug.	
The relationship of an adverse event may be considered “no reasonable possibility” if it is clearly due to extraneous causes or if at least 2 of the following apply:
 
 • It does not follow a reasonable temporal sequence from the administration of the study drug. • It could readily have been produced by the subject’s clinical state, environmental or toxic factors, or other modes of therapy administered to the subject. • It does not follow a known pattern of response to the study drug. • It does not reappear or worsen when the study drug is re-administered.
Reasonable possibility (related)	This category applies to adverse events for which, after careful medical consideration at the time they are evaluated, a connection with the study drug administration cannot be ruled out with certainty.	
The relationship of an adverse event may be considered “reasonable possibility” if at least 2 of the following apply:
 
 • It follows a reasonable temporal sequence from administration of the study drug. • It cannot be reasonably explained by the known characteristics of the subject’s clinical state, environmental or toxic factors, or other modes of therapy administered to the subject. • It disappears or decreases on cessation or reduction in dose. There are important exceptions when an adverse event does not disappear after discontinuation of the study drug, yet a drug relationship clearly exists. • It follows a known pattern of response to the study drug.

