7.1.5.3. Reporting a Serious Adverse Event

7.1.5.3.1. Investigator Responsibility

To satisfy regulatory requirements, all serious adverse events (as described in Section 7.1.5.1) that occur during the study period (including the protocol-defined follow-up period, described in Section 7.1.2), regardless of judged relationship to treatment with the study drug, must be reported to the sponsor by the investigator. The event must be reported within 24 hours of when

the investigator learns about it. Completing the serious adverse event form and reporting the event must not be delayed, even if not all the information is available. The investigator does not need to actively monitor subjects for adverse events once this study has ended.

Serious adverse events occurring to a subject after the treatment of that subject has ended should be reported to the sponsor if the investigator becomes aware of them.

The serious adverse event form should be sent to the sponsor's LSO in Germany (contact information is in the Clinical Study Personnel Contact Information section).

The following information should be provided to record the event accurately and completely:

- study number
- investigator and investigational center identification
- subject number
- onset date and detailed description of adverse event
- investigator's assessment of the relationship of the adverse event to the study drug (no reasonable possibility, reasonable possibility)

Additional information may include the following:

- age and sex of subject
- date of first dose of study drug
- date and amount of last administered dose of study drug
- action taken
- outcome, if known
- severity
- explanation of assessment of relatedness
- concomitant medication (including doses, routes of administration, and regimens) and treatment of the event
- pertinent laboratory or other diagnostic test data
- medical history
- results of dechallenge/rechallenge, if known
- for an adverse event resulting in death:
 - cause of death (whether or not the death was related to study drug)
 - autopsy findings (if available)

The investigator must ensure that the IEC/IRB is also informed of the event, in accordance with national and local regulations.

Each report of a serious adverse event will be reviewed and evaluated by the investigator and the sponsor to assess the nature of the event and the relationship of the event to the study drug, study procedures, and to underlying disease.

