7.1.8. Overdose of Study Drug

Any dose of study drug (whether the investigational product or tracers), whether taken intentionally or unintentionally, in excess of that prescribed must be immediately reported to the sponsor.

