3.2. Safety Analysis Set

The safety analysis set will include all subjects who receive at least 1 dose of study drug (pridopidine or PET Tracer). In this analysis set, treatment will be assigned based on the treatment subjects actually received.

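### Related-adverse-event tables by pridopidine dose can include PET tracer reactions, because study drug is used in two senses and no agent-specific causality rating is specified

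*Protocol*

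**What the plan says.** **Objective.** The safety objective in protocol 2.2.2 and SAP 1.1.1 concerns pridopidine.

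**Causality rating.** Protocol 7.1.4 defines one two-level scale: "The relationship of an adverse event to the study drug is characterized as follows". Section 7.1.2 asks the site to record more than that: "The relationship of each adverse event to study drug and study procedures". The serious adverse event report in 7.1.5.3.1 requires the investigator's "assessment of the relationship of the adverse event to the study drug (no reasonable possibility, reasonable possibility"), and the joint review with the sponsor in the same section considers "the relationship of the event to the study drug, study procedures, and to underlying disease".

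**Study drug including the tracer.** Protocol 7.1.8 has "Any dose of study drug (whether the investigational product or tracers"). SAP 3.2 builds the safety set from subjects with "at least 1 dose of study drug (pridopidine or PET Tracer"). SAP 7.2 adds the PET tracer in brackets after study drug where it sets the start of event counting.

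**Study drug meaning pridopidine.** Protocol 3.9.1 says there is no study drug besides pridopidine. Sections 3.10.1, 5.1.2 and 5.1.3 equate the two. Section 7.1.5.2 names the pridopidine Investigator's Brochure as the only reference safety information.

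**Tabulation.** The Synopsis (Safety Analyses) and protocol 9.10.2 plan summaries of "adverse events determined by the investigator to be related to study treatment (ie, reasonable possibility"), and 9.10.2 points the related-event summary to the 7.1.4 rating. SAP 7.2 presents events by part, cohort and population total, and SAP 4.1 defines cohort as dose level combined with population. SAP 7.2 treats a missing relationship as related.

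**The concern.** A reader will take the related-event columns, headed by pridopidine dose, as pridopidine-related events. The plan does not guarantee that. If investigators read study drug to include the tracer, a suspected tracer reaction is marked related and lands under a pridopidine dose. If they read it as pridopidine alone, a suspected tracer reaction has no defined drug-causality rating, and a related event in Part 0, where no pridopidine is given, has no meaning.

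The tracer cannot simply be ignored. Protocol 1.4.2.2 says of fluspidine that "it is possible that there are unknown risks with the use of this tracer", and section 7.9 provides for evaluating injection-site reactions. Section 7.1.5.3.2 also foresees updating the listings of expected toxicities for pridopidine, which needs a judgement specific to pridopidine.

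**Working it through.** **1. Interval between the two agents at visit 3.** Protocol 3.1 starts PET session 2 at 2 hours after pridopidine, and tracer injection coincides with the start of the first 90-minute block. Check: 2 h + 1.5 h = 3.5 h, which matches the end of the first scan given in Table 1 (ECG footnote) and section 7.6. The 90 minutes in that footnote fits the pre-tracer ECG. If it were the injection time, the scan would end at 1.5 h + 1.5 h = 3.0 h, which does not match.

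**2. Exposures.** A Part A or B subject completing both sessions has 2 tracer injections (visits 2 and 3) and 1 pridopidine dose (visit 3). A Part 0 subject has 2 fluspidine injections and no pridopidine.

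**3. Where a Part A or B event goes.** SAP 7.2 starts counting at the first tracer dose, and the column is the subject's pridopidine dose cohort. By onset:

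| Onset | Agents given so far | Column in SAP tables | Separable by onset time? |
|---|---|---|---|
| After visit 2 injection, before pridopidine | Tracer only | Pridopidine dose cohort | Yes |
| Visit 3, after pridopidine, before injection | Pridopidine, plus the earlier visit 2 tracer | Pridopidine dose cohort | Yes, from the visit 3 injection |
| Visit 3, after injection | Both, about 2 h apart | Pridopidine dose cohort | No |

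The first row can be separated using the onset dates and times required by protocol 7.1.2, but no planned table does so. SAP 7.2 mentions a treatment assignment for events only in a missing-time rule and does not define the treatments. For the last row, only an agent-specific judgement by the investigator helps, and neither document describes one.

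**4. Does the procedures item fill the gap?** Relationship to study procedures is to be recorded, but 7.1.4 gives no scale for it, neither 9.10.2 nor SAP 7.2 summarises it, and nothing says whether a tracer injection is a procedure or a drug dose. As written, it does not separate the agents.

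**5. Size of one misplaced event.** Cohorts have up to 4 subjects: 1/4 = 25%. With 3 subjects: 1/3 = 33%. These show how far one event moves a column; they say nothing about how likely such an event is.

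**The case against.** The strongest reply is that the narrow meaning may be the operative one. The product, storage and tracer-administration sections all use study drug for pridopidine, and the reference safety information is pridopidine's. The inclusive wording in protocol 7.1.8 concerns overdose reporting, and that in SAP 3.2 concerns entry to the safety set, where it brings in Part 0. The SAP's precedence over the protocol does not rewrite a rating made at the site. On this reading an investigator could call a tracer reaction unrelated, since 7.1.4 allows for other therapies as a cause, and the dose columns would stay clean.

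Much of this stands. A reader might infer that the tracer is definitely part of the rated drug, that causality is recorded only once, and that the suspected agent is lost at data entry. The documents support none of these: the term is used both ways, relationship to procedures is also recorded, and the CRF is not among the documents and may already have separate fields. Nor is it right that timing never helps; step 3 shows where it does.

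Other mitigation is real. All events are listed and cohorts are small enough to read by subject. Part 0 is tabulated separately and gives a tracer-only reference for fluspidine, although in few subjects (up to 6 in protocol 3.1, 3 in SAP 2.1), with no counterpart for fallypride. The protocol expects the tracer mass to have no pharmacological effect, reports no ill effects attributed to either tracer so far, and expects minimal risk from fallypride.

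What the reply does not do is make the plan work. SAP 7.2, the section that defines the adverse-event tables, itself counts the tracer as study drug, and the narrow reading leaves tracer reactions without a drug rating.

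**Conclusion.** The point holds in limited form. The meaning of study drug is unsettled, no causality rating specific to pridopidine or to the tracer is described, and the related-event tables by dose can therefore include tracer-attributed events. The documents do not show that they will.

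The overlap that onset times cannot resolve is confined to events after the visit 3 injection. Visit 2 events can be separated, but the planned tables do not separate them. One misplaced event is 25% of a full cohort of 4, or 33% of 3. The objective affected is secondary and descriptive, so no test or error rate is at stake, only the interpretation of the safety tables. The conclusion assumes that the CRF and SAE form follow the protocol text; if they already hold agent-specific answers, only the definitions and the table rules need changing.

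**What to change.** 1. Define study drug once and use it the same way in the protocol and SAP, with separate terms for pridopidine and PET tracer.
2. Unless the CRF and SAE form already do so, record causality as three separate answers: pridopidine, PET tracer, study procedure. State which category tracer injection belongs to.
3. In protocol 9.10.2 and SAP 7.2, base the related summaries for Parts A and B on causality to pridopidine, for events starting after the pridopidine dose. Impute a missing relationship as pridopidine-related only for those events.
4. Tabulate tracer-related events, including visit 2 tracer-only events, separately for Parts 0, A and B.

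The cost is a CRF field if not already present, plus protocol and SAP wording. Some visit 3 events will be rated related to both agents and appear in both tables; that ambiguity is genuine and is better shown than merged.

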AUC _{0-t}	area under the concentration × time curve from time 0 to time of last measurable concentration
BCRP	breast cancer resistance protein
BDNF	brain-derived neurotrophic factor
bid	twice daily
BMI	body mass index
BP	blood pressure
BP _{ND}	regional binding potential
BUN	blood urea nitrogen
CAG	cytosine-adenosine-guanine
C _{average}	average plasma concentration
CDMS	clinical data management system
CFR	Code of Federal Regulations (US)
C _{max}	maximum observed concentration
CNS	central nervous system
CPK	creatine phosphokinase
CPP	clinical project physician
CRF	case report form (refers to any media used to collect study data [ie, paper or electronic])
CRO	contract research organization
CSR	clinical study report
C-SSRS	Columbia-Suicide Severity Rating Scale
CYP	cytochrome P450
D2R	dopamine-2 receptor
DHEA	dehydroepiandrosterone
DNA	deoxyribonucleic acid

Abbreviation	Term
DSM-5	Diagnostic and Statistical Manual of Mental Disorders, Fifth Edition
DSMB	Data and Safety Monitoring Board
EC ₅₀	plasma concentration corresponding to 50% of E _{max}
EC ₈₀	plasma concentration corresponding to 80% of E _{max}
ECG	electrocardiography, electrocardiogram
EC _{opt}	plasma concentration corresponding to optimal receptor occupancy
EDTA	ethylenediaminetetraacetic acid
EM	extensive metabolizer
E _{max}	an asymptote representing the maximum receptor occupancy
ET	early termination
EU	European Union
FDA	Food and Drug Administration (US)
FU	Follow up
GCP	Good Clinical Practice
GGT	gamma-glutamyl transpeptidase
GMP	good manufacturing practice
HART	Huntington's disease ACR16 Randomized Trial
HBsAg	hepatitis B surface antigen
HD	Huntington's disease
HDL	high density lipoprotein
HIV	human immunodeficiency virus
IB	Investigator's Brochure
IC ₅₀	half maximal inhibitory concentration
ICH	International Council for Harmonisation
IEC	Independent Ethics Committee
IMP	investigational medical product
IND	Investigational New Drug
IRB	Institutional Review Board
IUD	intrauterine device
LDH	lactate dehydrogenase
LDL	low density lipoprotein
LLOQ	lower limits of quantification
LSO	local safety officer
MAD	multiple ascending dose

Abbreviation	Term
MATE1	multidrug and toxin extrusion protein 1
MATE2K	multidrug and toxin extrusion protein 2-K
MedDRA	Medical Dictionary for Regulatory Activities
MermaiHD	Multinational European Multicentre ACR16 study in Huntington's Disease
mMS	Modified Motor Score
MR-AC	MRI-based Attenuation Correction
MRI	magnetic resonance imaging
MRS	magnetic resonance spectroscopy
MTD	maximum tolerated dose
n	number
NDA	New Drug Application
NOAEL	no observed adverse effect level
OAT1	organic anion transporter 1
OAT3	organic anion transporter 3
OATP1B1	organic anion transporting polypeptide 1B1
OATP1B3	organic anion transporting polypeptide 1B3
OCT1	organic cation transporter 1
OCT2	organic cation transporter 2
OTC	over-the-counter
PET	positron emission tomography
P-gp	P-glycoprotein
PI	principal investigator
pi	post-injection of tracer
PM	poor metabolizer
qd	once daily
QTcF	Fridericia-corrected QT interval
RBC	red blood cell
RNA	ribonucleic acid
RO	receptor binding/occupancy
rs-fMRI	resting state functional magnetic resonance imaging
RSI	reference safety information
S1R	sigma-1 receptor
SD	standard deviation
SOC	system organ class

Abbreviation	Term
SOP	standard operating procedure
SUSAR	suspected unexpected serious adverse reaction
$t_{1/2}$	terminal elimination half-life
T1 MPRAGE	T1-weighted rapid 3-dimensional gradient-echo technique
t_{max}	time to reach maximum (peak) concentration
TMS	Total Motor Score
TV-45065	main metabolite of pridopidine
UHDRS	Unified Huntington's Disease Rating Scale
ULN	upper limit of normal
US(A)	United States (of America)
V	visit
V_d/F	apparent volume of distribution of the drug following extravascular administration
V_{ND}	global non-displaceable volume of distribution
V_T	PET total volume of distribution
WBC	white blood cell
WHO	World Health Organization
WHO Drug	World Health Organization (WHO) drug dictionary

